Following Randomization: After random assignment, participants will begin Tai Chi or Wellness treatment (12 weeks twice each week), half to each condition. Participants may be given a water bottle after attending Tai Chi or Wellness class. The water bottles have a logo that says "Whole Health Study" and display the Operation Desert Storm and Operation Desert Shield ribbon and the circular VA emblem. These water bottles may be mailed to participants with a thank you note from the study team. Participants engaged in the study at the 9-month follow-up assessment may also receive a 25th Anniversary Gulf War Challenge Coin. These coins may be mailed to participants with a thank you note from the study team. Participants in both conditions will receive assessments at baseline, 12 weeks (post-intervention), 24 weeks (approximately 3 months post-intervention) and 48 weeks (approximately 9 months post-intervention). (See Table 1 above.) Weekly measures will be collected by study staff via telephone and entered into a secure database remotely. Weekly measures may be mailed or e-mailed (via encrypted email messages) to participants so they can easily follow along with the weekly measure assessments. At the time of the collection of these weekly measures, feedback regarding preferences and areas for group improvement may be solicited from participants as

needed. This could include topics such as: best ways to maximize telehealth visibility and at-home Tai Chi setup; any feedback to relay to the instructor; preferences for the amount of sitting vs. standing for the class; preferences for the amount of group discussion vs. didactic instruction, etc. In addition, participants will be sent resources (e.g., VA Boston Whole Health handouts, IRB-approved virtual health resources) for continued engagement in health practices outside of group. This information will be recorded in an Excel spreadsheet that will use subject ID identifiers only and will be saved to a previously approved folder in the Drive: "[\\r04bhsnas61\resgroups\\$\PTSD\DATA\RESEARCH\TeleHealth](#) - [name]\Tai Chi Studies\Gulf War Study\Data". Information will be discussed at weekly lab meetings to help the study team improve the TeleHealth experience for group participants.

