complete all assessments. In order to provide incentive to complete the follow-up assessments and to compensate participants for ongoing commitment to the research project, participants will receive additional compensation for the later assessments. Although rigorous attempts will be made to keep participants in the study and to gather complete data at each of the scheduled assessments, we conservatively anticipate up to 20% attrition and other incomplete data at the 12-week assessment due to factors outside our control (e.g. participant unwillingness, time constraints). In addition to planning for dropouts a priori by recruiting a larger sample, we plan to conduct intent-to-treat analyses (see below) to protect against potential bias that may occur when individuals drop out of the study due to their level of disability and their response to treatment and by using imputation methods for missing data as described below.

Data and Power Analysis for Sub-Study II

With 80 participants in the telehealth study (40 in each condition), assuming that 15% would not complete the post-treatment assessment, we would have sufficient (.80) power to show a medium-large between group effect (0.69). Importantly, we would also have .80 power to detect a medium (0.5) within-group effect.

Data Analyses for Specific Aims

The goal of the primary analysis is to determine whether participants in the Tai Chi Condition show more advantageous change in Brief Pain Inventory scores from baseline to 12-week assessment than those in the Wellness Condition. The analysis will follow an intent-to-treat approach (all randomized patients will be included in the analysis). The primary analysis will compare groups on the change from baseline Brief Pain Inventory to 12-week using generalized estimating equation (GEE) analysis of covariance adjusting for baseline score. The GEE analysis model will incorporate change from baseline to all patient visits through 12-week into the analysis, and will include main effects of treatment, visit, and the baseline score, and a treatment-by-time interaction effect. From this model, an assessment of the treatment difference on mean change from baseline to 12 weeks will be carried out on the robust estimates using a two-sided 0.05 level of significance. An unstructured correlation structure will be assumed as the within-patient correlation between time points.

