The primary analysis will be based on all available data. However, as supportive analyses, missing Brief Pain Inventory scores will be imputed at each visit in a monotone manner via multiple imputation linear regression approach and the above analysis will be repeated on the imputed data. Specifically, the imputation model will include important covariates such as age, gender, and baseline Brief Pain Inventory score. A total of 10 imputed datasets will be generated, and the above GEE analysis will be carried out on each imputed dataset; the Week 12 score results will be combined across the 10 datasets using the standard techniques for multiply imputed data sets in order to yield on overall Week 12 on the imputed data.

Similar analyses will be used for secondary endpoints. We anticipate that the distribution of the pain scale and scores on secondary outcome measures will be skewed, and that log transformed scores will be used in the analysis.

Human Subjects Research

a. Human Subjects Involvement and Characteristics

The participant population is to be comprised of up to 140 male and female Gulf War Veterans. These individuals will be recruited on a volunteer basis. Only individuals who provide written informed consent may participate. A participant may withdraw his/her consent at any time and without prejudice. A clear and detailed explanation will precede all procedures.

Informed consent will be obtained by the study PI or by another IRB-approved study staff member prior to the initiation of any study procedures. Informed consent will be reviewed with the participant at the beginning of this scheduled appointment, prior to initiating the assessment.

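### Does the Sub-Study II power statement understate expected loss by assuming 15% non-completion when the attrition section allows up to 20%?

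*Combined protocol and SAP*

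**What the plan says.** The section Data and Power Analysis for Sub-Study II opens "With 80 participants in the telehealth study (40 in each condition") and goes on: "assuming that 15% would not complete the post-treatment assessment, we would have sufficient (.80) power to show a medium-large between group effect (0.69"). It adds that "we would also have .80 power to detect a medium (0.5) within-group effect". It names no test, no alpha and no baseline correlation.

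The section immediately before it, Participant Attrition and Missing Data, states: "we conservatively anticipate up to 20% attrition and other incomplete data at the 12-week assessment". It is not specific to either sub-study. It names three protections: recruiting more participants than needed, intent-to-treat analysis and imputation.

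Data Analyses for Specific Aims sets the primary test at a two-sided 0.05 level, "using generalized estimating equation (GEE) analysis of covariance adjusting for baseline score". It also says "The GEE analysis model will incorporate change from baseline to all patient visits through 12-week into the analysis", and that "The primary analysis will be based on all available data". The schedule of measures lists the Brief Pain Inventory weekly during treatment, and the section Following Randomization says "Weekly measures will be collected by study staff via telephone and entered into a secure database remotely".

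**The concern.** Two loss rates for the same time point stand one section apart. The plan calls the higher one conservative, yet it computes power only at the lower one and does not say why. The between-group figure also appears to have no slack: 34 per arm is the smallest number that reaches 0.80 at an effect of 0.69, and 34 is exactly what 15% loss from 40 leaves. This pattern can mean that a loss rate was picked to make the answer come out at 0.80.

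If so, readers would be given too favourable a view of what Sub-Study II can detect. The paragraph matters because Sub-Study I is already described as having low power, so the between-group comparison rests on Sub-Study II.

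**Working it through.** **Inputs.** From the power section: 40 per arm, 15% non-completion, effects of 0.69 (between) and 0.5 (within), power 0.80. From the attrition section: up to 20%. From the primary analysis: two-sided alpha 0.05. Effects are standardised, since the plan gives no raw SD.

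**Method.** Power comes from the noncentral t distribution:
- between groups: noncentrality d × √(n/2), with 2n − 2 degrees of freedom;
- within group: noncentrality d × √n, with n − 1 degrees of freedom.

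**Step 1: reproduce the stated figures.** 40 × 0.85 = 34 per arm.
- Between: 0.69 × √(34/2) = 2.845 on 66 df; power 0.8005. The effect detectable at exactly 0.80 is 0.6896.
- Within: 0.5 × √34 = 2.915 on 33 df; power 0.808. The effect detectable at 0.80 is 0.495.

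Both match the plan.

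**Step 2: take the full 20% as lost completers.** 40 × 0.80 = 32 per arm.

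| | 34 per arm | 32 per arm |
|---|---|---|
| Between, power at 0.69 (t) | 0.8005 | 0.776 |
| Between, power at 0.69 (normal approximation) | 0.812 | 0.788 |
| Within, power at 0.5 (t) | 0.808 | 0.782 |
| Within, power at 0.5 (normal approximation) | 0.830 | 0.807 |
| Between, effect at 0.80 power (t) | 0.690 | 0.711 |
| Within, effect at 0.80 power (t) | 0.495 | 0.511 |

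The between-group figure falls 0.8005 − 0.776 ≈ 0.025, and the detectable effect rises by about 0.02. The within-group figure falls below 0.80 only with the t-test.

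**Step 3: test the charge of no margin.** One completer fewer (34 and 33) gives 0.794 at 0.69; one fewer per arm (33 and 33) gives 0.788. But 0.69 is the effect solved for at 0.80 power with 34 per arm (0.6896, rounded). An effect obtained that way has no slack at any sample size. Repeating the exercise for totals of 60, 70, 80, 100 and 120 at 15% loss, and removing one completer per arm each time, gives power of 0.784 to 0.792 at the solved effect. The feature belongs to reporting a detectable effect, not to this plan. It would tell us something only if 0.69 had been justified separately as a target, and the documents do not present it so.

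**Step 4: compare with the planned test.** The primary model adjusts for baseline. The plan gives neither the baseline correlation r nor the SD unit of 0.69, so both are assumptions here. With 32 per arm and 61 df:
- 0.69 in week-12 SD units, effective size 0.69/√(1 − r²): power 0.792, 0.801, 0.813 and 0.880 at r = 0.2, 0.25, 0.3 and 0.5.
- 0.69 in change-score SD units, effective size 0.69 × √(2/(1 + r)): power 0.930, 0.880, 0.838, 0.817 and 0.796 at r = 0.25, 0.5, 0.7, 0.8 and 0.9.

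Under either unit, any r from about 0.25 to 0.88 keeps between-group power at or above 0.80 even at 20% loss. In addition, a participant who misses week 12 can still contribute weekly pain scores to the model.

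**The case for a change.** The best argument for the concern is the trial's own experience. The section on splitting the study reports that 43 of 53 Sub-Study I participants (81%) completed the post-treatment assessment, a loss of 10/53 = 19%. Applied to 40 per arm, that leaves 40 × 43/53 = 32.45 completers per arm and unadjusted between-group power of about 0.78. It is the only completion rate from this trial in the documents, and it is nearer to 20% than to 15%. For an unadjusted test of week-12 scores, a missing score removes the participant whatever the cause, so the broader scope of the 20% does not fully answer the point. Nor does baseline adjustment help the within-group figure, which the plan itself stresses.

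All of that is correct, but it does not make a defect. Sub-Study I was delivered in person and was stopped by the 2020 halt, and the protocol says the two versions differ too much to combine. Its loss rate makes 19% plausible for telehealth without showing that 15% is wrong. Accepting 19% or 20% in full moves the detectable effects only to about 0.71 and 0.51.

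The power paragraph also makes no allowance for group delivery, which would lower power. With groups of 6 and an assumed intraclass correlation of 0.01 to 0.05, unadjusted between-group power would be about 0.78 to 0.71 at 34 per arm and 0.76 to 0.68 at 32. That is a separate question. It applies at either loss rate and does not bear on the choice between them.

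**Conclusion.** The concern does not hold. The power statement is correct for the rate it declares. Its 15% non-completion lies within the general ceiling of up to 20%, which also counts other incomplete data, so the two sections do not contradict each other. The lack of slack follows from solving for an effect at 0.80 power and would appear at any sample size.

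What is left is a wish for one more sensitivity figure. On the least favourable reading (all 20% lost as completers, two-sided t-tests at 0.05, no baseline adjustment), power is about 0.78 in place of 0.80, and the detectable effects are 0.71 in place of 0.69 and 0.51 in place of 0.50. No loss of power is shown for the planned baseline-adjusted analysis of all available data: between-group power stays at or above 0.80 at that bound for any assumed baseline correlation from about 0.25 to 0.88. Such a figure would correct nothing in the plan and would not change enrolment, analysis or interpretation.

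### The primary GEE test relies on robust standard errors with about 34 patients per arm, but the plan names no small-sample correction or reference distribution; the usual default would run at about 6%, not 5%

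*Combined protocol and SAP*

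**What the plan says.** All of this is in the combined protocol and SAP.

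- *Data Analyses for Specific Aims*: the groups are compared on change in Brief Pain Inventory (BPI) score "using generalized estimating equation (GEE) analysis of covariance adjusting for baseline score". The model "will include main effects of treatment, visit, and the baseline score, and a treatment-by-time interaction effect". On the working correlation: "An unstructured correlation structure will be assumed as the within-patient correlation between time points". The test of the week-12 difference "will be carried out on the robust estimates using a two-sided 0.05 level of significance".
- *Data and Power Analysis for Sub-Study II*: the size is given as "With 80 participants in the telehealth study (40 in each condition), assuming that 15% would not complete the post-treatment assessment". Power is put at 0.80 for a between-group effect of 0.69.
- *Splitting the Study into Two Sub-Studies*: the in-person data (53 randomised) are not combined with the telehealth data.
- *Statistical Plan and Data Analysis*: SPSS, SAS and R are named, but no procedure or option.
- The paragraphs after the primary model repeat the GEE in each of 10 imputed data sets and plan similar analyses for the secondary endpoints.

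No section states a small-sample variance correction, a t or F reference, or a degrees-of-freedom rule.

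**The concern.** The sandwich variance is justified in large samples. It is built from fitted residuals, which are on average smaller than the true errors, so it tends to understate the variance of the treatment contrast. A normal reference then ignores the fact that the variance is itself estimated. Both errors push towards rejection, and at about 34 patients per arm neither is negligible. An analyst who follows the plan literally could report a test labelled 5% whose actual level is somewhat higher, with an interval somewhat too short. The same would carry into the secondary outcomes and the imputed analyses. Because the plan is silent, the primary p-value would also depend on a software option that could be chosen after the data are seen.

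**Working it through.** **Inputs from the plan.** 80 patients, 1:1, 15% without week-12 data: 80 × 0.85 / 2 = 34 per arm. Two-sided 0.05. Elsewhere (*Participant Attrition and Missing Data*) up to 20% loss is anticipated: 80 × 0.80 / 2 = 32 per arm.

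**Assumed, not in the plan.** Normal outcomes, random dropout, the within-patient correlations, and the number of visits in the model. The plan says "The GEE analysis model will incorporate change from baseline to all patient visits through 12-week into the analysis", and the assessment table has the BPI collected weekly during treatment, so the number of post-baseline time points could be anything from 1 to about 13.

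**Step 1: the plan's own power.** A two-sample t-test with 34 per arm and effect 0.69 has power 0.8005 (0.812 by the normal formula). A one-sample t-test with n = 34 and effect 0.5 has power 0.808. The stated figures reproduce.

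**Step 2: closed form, week 12 only, no covariate.** With n per arm, the uncorrected sandwich standard error is the usual one times √((n−1)/n). Rejecting when the ratio exceeds 1.96 therefore gives an actual level of

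P(|t with 2n−2 df| > 1.96 × √((n−1)/n)).

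At n = 34: 1.96 × √(33/34) = 1.931 on 66 df, giving 5.78%. At n = 32 it is 5.83%, and at n = 40 (no loss) 5.66%.

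**Step 3: interval width.** At n = 34 the exact interval is wider than the uncorrected one by the factor (1.997 / 1.960) × √(34/33) = 1.034. The uncorrected interval is thus 1 − 1/1.034 = 3.3% too narrow (3.5% at n = 32). A reported p of 0.050 corresponds to 0.058.

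**Step 4: simulation under the null of the model with baseline covariate, N = 80.** Rejection rates in percent (KC = Kauermann-Carroll, MD = Mancl-DeRouen):

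| Post-baseline visits, dropout | Runs | Uncorrected, normal | Uncorrected, t | KC, t | MD, normal | MD, t |
|---|---|---|---|---|---|---|
| 1, none | 20,000 | 5.7 | 5.4 | 4.9 | 4.9 | 4.6 |
| 1, 15% | 20,000 | 5.9 | 5.45 | 4.9 | 4.8 | 4.4 |
| 1, 20% | 20,000 | 6.1 | 5.6 | 5.0 | 4.9 | 4.5 |
| 3, 15%, unstructured | 8,000 | 6.0 | 5.5 | 5.1 | 5.05 | 4.7 |

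The Monte Carlo standard error is about 0.17 points with 20,000 runs and 0.27 with 8,000. Separate code with 15% dropout gave 6.2% for one visit (8,000 runs) and 6.1% for three (6,000 runs) for the uncorrected normal test. In the one-visit case the mean robust standard error was 0.1908 against a true standard deviation of 0.1977, a ratio of 0.965.

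**Step 5: many visits.** With 13 visits, unstructured correlation, 15% dropout and exchangeable data, the uncorrected test rejected 7.0%, and the corrected tests 5.7% (MD, t) to 6.0% (KC, t), with a standard error of about 0.5. Without dropout the uncorrected rate was 6.1%. Other runs with 12 visits gave 5.8 to 6.0% uncorrected and 4.4 to 4.6% for MD with t. Under a different assumed covariance with 12 or 13 visits, the unstructured matrix was not positive definite in 60 to 77% of runs. These results do not settle a figure.

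**The case against.** **The plan never says uncorrected, and never says normal.** This stands. It speaks only of robust estimates. A reader might infer that the planned test has a true level of 6%, but the documents do not support that as a statement of fact. With a t reference alone the rate is about 5.5%, and with Kauermann-Carroll and t about 5%. The detectable effect of 0.69 is the t-test solution at 34 per arm (0.690, against 0.679 from the normal formula), so the sizing was not done on the normal scale. That does not show which reference the GEE test would use. What remains is that the choice is open and the ordinary form of the analysis does not hold its level.

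**The excess is very small.** This also stands: 0.7 to 1.2 points with few visits. Reading it as a threat to the primary conclusion in general would go too far.

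**80 is not a cap.** Correct: it is the planning figure, and *Overview and Study Flow* allows up to 140. If that ceiling covers both sub-studies, 140 − 53 = 87 remain, about 37 per arm after 15% loss, and the closed form gives 5.7%. The conclusion is unchanged.

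**A correction can overshoot.** True of Mancl-DeRouen combined with t, at 4.4 to 4.7% with few visits. The plan also expects skewed scores and log transformation. In a one-visit check with untransformed lognormal data, the uncorrected test rejected 5.6% and Mancl-DeRouen with t only 3.9%. This is a reason to choose the combination with care.

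**Weekly scores might make it much worse.** A reader might infer this from the 7.0% figure. The many-visit results depend on an assumed covariance and do not agree with one another, so they do not support a firm statement.

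**Conclusion.** The point holds as a minor gap in the specification. The primary test rests on robust estimates with a planned 80 patients, and the plan gives neither a small-sample correction nor a reference distribution. If the uncorrected sandwich variance is used with a normal reference, the actual two-sided level is about 5.7 to 6.2% with one to three post-baseline visits, and the 95% interval is roughly 3 to 4% too narrow. Only a borderline p-value would be affected. The closed form rests on normal data and a comparison without covariate; the simulations rest on normal data and random dropout. The level with weekly visits in the model is uncertain, with or without a correction. Correlation between patients treated in the same class was not modelled and is a separate matter.

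**What to change.** Add one sentence to *Data Analyses for Specific Aims*: the week-12 treatment contrast is tested with a Kauermann-Carroll bias-corrected sandwich variance and a t reference, with degrees of freedom equal to the number of patients contributing data minus the number of between-patient parameters. With week 12 only and 68 completers, that is 68 − 3 (intercept, treatment, baseline) = 65. Mancl-DeRouen with a normal reference is an acceptable alternative; Mancl-DeRouen with t is somewhat conservative here. Apply the same rule to the secondary outcomes and within each of the 10 imputed data sets before pooling, and name the software procedure and option.

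The cost is an option or add-on in the software and intervals a few percent wider. The stated power already matches a t-test at 34 per arm, so the sample size need not change on this account. If the weekly scores enter the model, the correction may not bring the level fully back to 5%.

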Splitting the study into two parts has important implications for data analysis and the interpretation of our results. In March 2020, we had randomized 53 participants (27 to Tai Chi and 26 to Wellness) in Sub-Study I and 43 (81%) completed post-treatment assessments. This number falls substantially short of the original target of enrolling 120 Gulf War veterans and the administrative halt on research precluded us from continuing to enroll to approach the enrollment target. As a result, the power to detect differences between the two intervention groups is low, an unfortunate consequence of low enrollment due to a restricted sample of Boston-area GW Veterans and the premature termination of the study. Analysis of data from Sub-Study I would include examination of the rich qualitative interview and satisfaction data we have collected as well as within-group changes on outcome measures. We expect that this will yield important results that will guide future studies. [name], the Scientific Program Officer for Gulf War studies, has approved this change to the analytic plan for our study.

Participant Attrition and Missing Data

Based on results from previous studies conducted by the PI with medical populations and with Tai Chi and physical activity interventions, it is anticipated that a high rate of participants will complete all assessments. A high rate of completion is also anticipated since participants will be compensated for their assessments and will have established rapport with study personnel. Participants who drop out of treatment will be encouraged to remain in the study and to

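### Ten imputations give a valid supportive analysis but leave a borderline supportive p-value dependent on the random seed; 100 would largely cure this

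*Combined protocol and SAP*

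**What the plan says.** The section Data Analyses for Specific Aims makes the week-12 treatment difference in Brief Pain Inventory (BPI) change the primary comparison. It is estimated by GEE and tested "using a two-sided 0.05 level of significance". On missing data the section says "The primary analysis will be based on all available data", and then that "as supportive analyses, missing Brief Pain Inventory scores will be imputed at each visit in a monotone manner". The number of imputations is fixed: "A total of 10 imputed datasets will be generated". The week-12 results are pooled by the usual combining rules. The covariates named for the imputation model are age, gender and baseline BPI, given as examples. No seed, imputation software or check of Monte Carlo error is stated, and no decision rule is attached to the imputed p-value.

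Three places bear on how much will be missing at week 12:
- Data and Power Analysis for Sub-Study II plans 80 participants, 40 per arm, "assuming that 15% would not complete the post-treatment assessment".
- Participant Attrition and Missing Data says "we conservatively anticipate up to 20% attrition and other incomplete data at the 12-week assessment".
- Splitting the Study into Two Sub-Studies reports that in the in-person part "43 (81%) completed post-treatment assessments" out of 53 randomized.

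**The concern.** Multiple imputation draws the missing values at random, so a rerun with another seed gives a slightly different estimate, standard error and p-value. Ten imputations are often judged by the efficiency of the point estimate, but efficiency does not measure how far the p-value moves between runs. The supportive analysis is there to show whether the primary result holds up when missing scores are filled in. If its p-value falls near 0.05, whether it appears to agree with the primary test may depend partly on the seed. At stake is the reading of a supportive result, not the primary conclusion.

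**Working it through.** **Inputs from the documents.** m = 10 imputations; 80 participants, 40 per arm; 15% missing at week 12 in the power calculation and up to 20% in the attrition section; Sub-Study I observed 43/53 = 81% complete, so 19% missing; two-sided 0.05; planned standardized effect 0.69.

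**The plan's own figure.** 40 × 0.85 = 34 per arm. A two-sample t-test with 34 per arm and effect 0.69 has power 0.800, which matches the stated .80.

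**Assumed input.** The documents give no FMI. In simulated 80-patient trials with regression imputation, FMI was about 0.16 at 15% missing and 0.21 at 20% missing when only baseline covariates were used. It was about 0.08 and 0.11 when an earlier BPI score (assumed correlation about 0.8 with week 12) was in the imputation model. The table of measures shows the BPI collected weekly during treatment, so the lower pair is possible.

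**Efficiency.** Relative efficiency is 1/(1 + FMI/m). At m = 10:
- FMI 0.16: 1/1.016 = 98.4%
- FMI 0.21: 1/1.021 = 97.9%

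**Movement of the estimate between seeds.** Its SD, in units of the standard error, is √(FMI/m):
- m = 10: √0.016 = 0.13 to √0.021 = 0.14
- m = 100: √0.0016 = 0.04 to √0.0021 = 0.05

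**Movement of the p-value.** Scale the total variance with unlimited imputations to 1, so the within part is 1 − FMI and the between part is FMI. For each rerun, draw the pooled estimate as t₀ + N(0, FMI/m) and the between-imputation variance as b = FMI × χ²(m−1)/(m−1). Then T = (1 − FMI) + (1 + 1/m)b, with small-sample (Barnard-Rubin) degrees of freedom from complete-data df 77 (80 less intercept, arm and baseline). The value t₀ is set so that the seed-free p is 0.04. For the planned effect over all results, t₀ is drawn from a normal distribution with mean 0.69 × √(34/2) = 2.84 and SD 1; for the null, with mean 0.

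| FMI | m | SD of pooled t | 95% rerun range of p (seed-free 0.04) | Reruns crossing 0.05 | Two seeds disagree, planned effect | Two seeds disagree, null |
|---|---|---|---|---|---|---|
| 0.08 | 10 | 0.10 | 0.026–0.063 | 19% | 3.2% | 1.2% |
| 0.08 | 100 | 0.03 | 0.035–0.046 | 0.1% | 1.0% | 0.4% |
| 0.11 | 10 | 0.12 | 0.024–0.070 | 24% | 3.9% | 1.5% |
| 0.11 | 100 | 0.04 | 0.034–0.047 | 0.5% | 1.2% | 0.5% |
| 0.16 | 10 | 0.15 | 0.020–0.081 | 31% | 5.0% | 1.8% |
| 0.16 | 100 | 0.05 | 0.032–0.050 | 2% | 1.5% | 0.6% |
| 0.21 | 10 | 0.18 | 0.018–0.092 | 35% | 6.1% | 2.2% |
| 0.21 | 100 | 0.06 | 0.031–0.052 | 4% | 1.8% | 0.7% |

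**Hand check at FMI 0.16, m = 10.** The df is (78/80) × 77 × 0.84 = 63. There t is 2.10 for p = 0.04 and 2.00 for p = 0.05, a gap of 0.10 against a seed SD of 0.15. That alone puts about one rerun in four over the line. The slightly larger standard error and fewer df at m = 10 bring it to 31%.

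**How narrow the band is.** With m = 10 and FMI 0.16 to 0.21, the chance of crossing 0.05 by seed-free p is: 0.01, 0.2% or less; 0.02, 1–4%; 0.03, 11–16%; 0.06, 25–27%; 0.08, 6–8%; 0.10, 1–2%.

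**Validity.** With m = 10 the pooled test rejects about 4.5% of the time under the null and 79% under the planned effect. With m = 100 the latter is 80%.

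**The case against.** The strongest reply is that nothing in the trial turns on this p-value. The 0.05 level is set for the primary GEE comparison, which uses the available data without imputation. A supportive analysis is read for consistency of estimate and interval, and the estimate moves between seeds by only about 0.13 to 0.14 of a standard error. Rubin's rules with small-sample df already allow for a finite number of imputations. All of this stands, and it keeps the point minor.

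A second reply is that the check uses a single week-12 comparison, whereas the plan repeats a robust GEE over all visits through week 12 and imputes visit by visit, so earlier BPI scores may well predict later ones. This also stands in part, and is why the lower FMI pair is shown. It does not remove the effect: at FMI 0.08 to 0.11, 19% to 24% of reruns still cross at a seed-free p of 0.04. The plan does not say that weekly scores enter the imputation model, and early dropouts may lack them.

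A third reply is that fixing a seed makes the result reproducible. It does, but the one reported p-value remains a draw from the same wide range. The plan lists several packages, and a seed does not carry from one to another.

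A reader might also infer that seeds disagree about a third of the time. Disagreement between two runs of 33% to 37% does arise with 10 imputations, but only among results selected in advance to have p between 0.03 and 0.08, in a single-visit model. In that band 100 imputations still leave 10% to 17%. It is not the rate over all results.

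**Conclusion.** The point holds as a minor one. Ten imputations are adequate for a valid and efficient estimate at 15% to 20% missing, but they leave a supportive p-value between about 0.03 and 0.08 noticeably dependent on the seed. Outside that band the dependence is slight.

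Two stronger readings are not supported. One is that 10 imputations make the imputed analysis invalid or badly inefficient; the rejection rates and efficiency above show otherwise. The other is that the trial's main conclusion could change with the seed; the primary GEE involves no imputation.

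The figures assume FMI between 0.08 and 0.21, complete-data df of 77, approximately normal scores, data missing at random and a single week-12 comparison. The direction does not depend on these assumptions; the size does.

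**What to change.** In Data Analyses for Specific Aims, change 10 to 100 in both places where the number of imputed datasets appears, and prespecify the random seed and the software and version that will run the imputation. If the imputed analysis is also meant for the secondary endpoints, which the plan says are analyzed similarly, apply the same number there. Scales such as the MFI-20, DASS-21 and ISI have no on-treatment measurement that could lower their FMI.

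The choice of 100 is a judgement about tolerable noise. At FMI 0.16 to 0.21 and a seed-free p of 0.04, it cuts crossing from 31–35% to 2–4%; 50 imputations would leave 8–12%.

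The cost is minutes of computing and one edited paragraph. Sample size, visits and the primary analysis are unaffected.
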